Rating of symptoms (dyspnea, cough, sore throat, headache, chest pain, and chest tightness) and blood pressure will also be measured. The selected symptoms were chosen because they have been recognized or are related to symptoms of ozone exposure (Lippmann, 1989). Dyspnea will be measured subjectively using a modified Borg scale that has previously been used to measure dyspnea and validated against other dyspnea measures (Gaber et al., 2019). The other symptoms will be subjective rated on a scale from 0-5. Blood pressure will be measured using an automated sphygmomanometer. In accordance with Hypertension Canada's guidelines on blood pressure measurement, blood pressure will be measured three times and the first measure will be thrown away while the latter two are averaged (Nerenberg et al., 2018).

Study Design

This research design can be characterized as a placebo-controlled crossover design with pre-post measures. There are two independent variables: ozone pollution status and medication status. The two levels of ozone pollution status are 170 ppb ozone and room air. The two levels of medication status are 200 µg of salbutamol and placebo medication. Participants will perform 30 minutes of submaximal exercise at 60% of their $VO_{2\max}$ in all four conditions. These conditions are salbutamol + ozone, placebo + ozone, salbutamol + room air, and placebo + room air. The order of the conditions on the experimental days will be randomized to one of four sequences. The four conditions will be labelled A (ozone + inhaler A), B (ozone + inhaler B), C (room air + inhaler A), and D (room air + inhaler B). The researchers will not know which inhaler (A or B) is placebo

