Participants will visit the lab on five occasions. It will also be expected that participants will take no leukotriene modifier medication (Singulair or Montelukast) 24 hours before each visit, no short acting beta agonists 8 hours before each visit, no long acting beta agonists 48 hours before each visit, and no anti-histamines 72 hours before each visit. These pre-visit restrictions control for potential confounding effects on the eucapnic voluntary hyperpnea (EVH) test and FeNO measurement. Participants will be asked to avoid supplementation with vitamin C, vitamin E, and multivitamins over the course of the 5 visits. This prevents changes in the response to ozone related to vitamin supplementation (Gomes et al., 2011). Finally, participants will be asked to avoid exercise 24 hours before each lab visit. This is to ensure there is no diminishment in asthma and/or EIB severity related to a refractory period following exercise (Stickland et al., 2012). Day one will be a screening day and will involve: obtaining consent, collecting height, weight, age, and sex, screening participants for EIB, conducting a $\text{VO}_{2\text{max}}$ test, and orienting participants to FeNO and spirometry measurement. Participants will re-read and sign a consent form in addition to reviewing and signing a PAR-Q+. They will then do practice spirometry and FeNO measurements to orient themselves to the procedure of these measures. Then, participants will complete a EVH test to screen for EIB. The EVH test requires participants to voluntarily hyperventilate regular air that has a higher than normal CO_2 concentration for 6 minutes to replicate breathing during exercise. This mimics the stimulus that leads to airway narrowing in EIB (Hull et al., 2016). The higher than normal CO_2 concentration prevents CO_2 levels in the blood from dropping leading to loss of consciousness. Spirometry measures are obtained before and after EVH and compared. A 10% or greater decrease in FEV_1 will be used to confirm the presence of EIB (Hull et al., 2016). Participants will then take salbutamol at the treatment dose (200 μg and perform a $\text{VO}_{2\text{max}}$ test on a cycle ergometer. Performing a $\text{VO}_{2\text{max}}$ text will allow for the exercise intensity to be standardized

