in subsequent trials at 60% of $VO_{2\max}$. A graded exercise test with a ramp protocol will be performed while expired gas is analyzed using a metabolic cart to measure $VO_{2\max}$ (Beltz et al., 2016). Participants will conduct a self-selected warm-up. Following the warm up, participants will start the exercise test at 75 or 100 Watts, with the workload increasing in a step-wise fashion by 10 or 20 Watts every two minutes until they feel that they can no longer continue or until they can no longer maintain a cadence of 60 rotations per minute (rpm). $VO_{2\max}$ will be considered achieved if three of the following four criteria are met: heart rate (HR) $>90\%$ of age-predicted maximum, respiratory exchange ratio >1.15 , plateau of oxygen consumption per minute (VO_2) with increasing work load, and volitional exhaustion (Beltz et al., 2016). Age-predicted maximum heart rate will be calculated as $220 - \text{age (years)}$.

Participants will return to the lab on four separate occasions to complete the four exercise trials in a random order. During each visit, participants will take two puffs from an MDI, wait 15 minutes, and then pre-exercise measures will be taken. Pre-exercise FeNO, blood pressure, and symptoms will be measured and then participants will put on a headset that includes a mouth piece that will be used for spirometry and will control inspired air during exercise. Pre-exercise spirometry will be measured and then participants will perform a self-selected warm-up. Once they are ready, participants will exercise at a resistance that will elicit 60% of their $VO_{2\max}$ for 30 minutes while breathing through a one-way valve connected to a sealed chamber. The chamber will either contain room air or 170 ppb ozone being generated by an ozone generator. After 5 minutes and 25 minutes of exercise participants will do an IC. After 30 minutes are complete, post-exercise blood pressure, symptoms, spirometry and FeNO will be measured. All visits will be separated by 48 hours to prevent carryover effects from previous exposure to ozone or salbutamol.

This 48-hour duration was chosen because it is longer than five half-lives of salbutamol medication.

Ethical Considerations

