risk related to ozone exposure would not exceed the level of risk that would occur in the daily lives of the participants. Participants will also have the ability to stop the exposure to ozone at any time. Some potential temporary side effects of salbutamol use include: nervousness, tremor, headache, dryness of the mouth, changes in taste or smell, cough, nausea, and dizziness. Some rare but serious side effects include: pounding heartbeat, chest pain, irregular heartbeat, rapid breathing, and confusion. Allergic reaction is rare but can result in rash, itchy tongue, severe dizziness, and trouble breathing (Burggraaf et al., 2001). This risk is avoided by only including participants in the study who have been prescribed salbutamol by their physician. A physician would not prescribe salbutamol if the side effects outweighed the benefits of the medication or the patient was allergic to the medication. If the participants do experience any serious side effects, immediate care will be provided by the researchers who are trained in standard first aid, and the participant will be taken to the nearest emergency room located approximately 250 meters away. On experimental days a physician will always be available to be onsite within ten minutes and at least one person collecting data will have a Standard First Aid with CPR/AED C certification. We have also created an emergency action plan and attached it to box 9.8.A of the application. This lab has a long track record of using this type of physician supervision with exercise studies in individuals with and without asthma, using higher intensity exercise, and even higher intensity exposures to air pollution like diesel exhaust ([H08-03055], [H09-01154], [H10-02028], [H10-00902], [H12-00539]). These studies have all been completed without incident. To ensure informed consent, a consent form will be sent to any individual interested in participating with enough time for them to review it and contact a member of the research team if they have any questions. This consent form will contain: the general purpose of the study and what the participant will be expected to do, foreseeable risks and potential benefits, alternatives to participation, contact information of the

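### The ten-minute physician cover and the CPR/AED C-certified data collector are promised only for experimental days, which leaves out the screening visit with the EVH and maximal exercise tests

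*Combined protocol and SAP*

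**What the plan says.** Ethical Considerations sets the supervision rule: "On experimental days a physician will always be available to be onsite within ten minutes". The rest of that sentence adds that at least one data collector will hold Standard First Aid with CPR/AED C certification.

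Study Design uses the same term for the randomised visits: "The order of the conditions on the experimental days will be randomized to one of four sequences". It sets the workload at those visits: "Participants will perform 30 minutes of submaximal exercise at 60% of their" VO2max, in each of the four conditions.

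Procedures names the first of the five visits differently: "Day one will be a screening day and will involve" consent, EIB screening, a VO2max test and practice measurements. The EVH test is done at that visit, and then "Participants will then take salbutamol at the treatment dose" before a graded test that runs "until they feel that they can no longer continue or until they can no longer maintain a cadence of 60 rotations per minute".

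**The concern.** The protocol picks out two safeguards and attaches them to a class of visit that, on its own usage, excludes day one. Ethical Considerations names EVH, together with exercise in ozone, as a point of higher risk for a severe asthma attack. It also lists fainting, heart rhythm disturbance and, rarely, heart attack as possible complications of maximal exercise. EVH and maximal exercise take place only on day one.

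Staff who follow the text could therefore schedule EVH and VO2max tests with no physician on call and no CPR/AED C-certified person present, while providing both for submaximal exercise in room air. What is at stake is participant safety.

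**Working it through.** The protocol gives no figure to reproduce here. The check compares wording across sections and then counts visits.

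**1. What the term covers.** *Experimental days* occurs twice: in the supervision sentence (Ethical Considerations) and in the randomisation sentence (Study Design). The second ties it to the days on which condition order is randomised. Procedures gives four such visits out of five. Day one is called a screening day in Procedures, and Measures/Instruments refers to an orientation day for practice spirometry. No section extends either safeguard to day one.

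**2. What happens on day one (Procedures).**
- Bronchodilators are withheld beforehand: "no short acting beta agonists 8 hours before each visit", and long-acting ones for 48 hours.
- EVH is done in that state. "Spirometry measures are obtained before and after EVH and compared", and a fall in FEV1 of 10% or more confirms EIB, so the test is meant to provoke airway narrowing.
- Salbutamol 200 µg is given after EVH and before the VO2max test. It lowers the bronchoconstriction risk of the maximal test but not that of EVH.
- PAR-Q+ is completed at this same visit. It identifies people who should see a physician before exercising; it provides no emergency response.

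**3. What still applies on day one.** Ethical Considerations states these without a day limit: rescue salbutamol, the participant's own medication, oxygen, the right to stop, an AED on site, researchers trained in standard first aid, and an emergency room about 250 m away. What is missing is the physician on ten-minute call and the CPR/AED C credential.

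**4. Visit count.** Inputs: 24 participants (Sample and Recruitment), 1 screening visit and 4 condition visits each, 2 of the 4 conditions in room air, everyone completing.

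| Visits | Calculation | Number | Two safeguards stated? |
|---|---|---|---|
| All | 24 × 5 | 120 | – |
| Condition visits | 24 × 4 | 96 | Yes |
| of which room air | 24 × 2 | 48 | Yes |
| Screening visits | 24 × 1 | 24 | No |

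The uncovered share is 24/120 = 20%, and it contains all 24 EVH tests and all 24 maximal tests of the enrolled participants. Each person who fails screening adds one more uncovered visit; the protocol gives no number for these.

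**The case against.** The strongest reply is that the phrase is loose, not restrictive. It is never defined, Study Design uses it only in passing, and nothing says a physician will be absent on day one. Shortly after the supervision sentence, the protocol cites the lab's long record with this kind of supervision, including at higher exercise intensity, which suggests a general practice. The emergency action plan (box 9.8.A of the ethics application) may set out cover visit by visit, and it is not in the documents. The risks of EVH and maximal exercise are also answered directly by the safeguards that have no day limit.

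Three narrower points have force:
- Ozone status is double-blinded, so room-air visits need the same cover as ozone visits. The 48 covered room-air visits are therefore not evidence of misplaced supervision. Half of them are placebo visits by people with asthma or EIB, so they are not trivial in risk.
- The certification part is the weaker half. A certificate belongs to a person and does not lapse between visits, and first-aid training is already required without a day limit.
- The 20% counts what a sentence covers. It does not measure the probability of harm, and the documents give no figure for that.

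These points limit the size of the concern and leave open what the authors intended. None of them points to text that extends the two safeguards to day one. Blinding explains why room-air visits are covered; it gives no reason to leave the screening visit out. If all visits were meant, the sentence still needs correcting, because staff schedule from it.

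**Conclusion.** The concern holds as a reading of the text. Two stated safeguards cover four of the five visits per participant and omit the one with the EVH test and the only maximal test. With 24 completers, that is 24 of 120 visits. Confidence is medium: the conclusion assumes that *experimental days* means the same in Ethical Considerations as in Study Design, and that the unseen emergency action plan does not already fill the gap. Only these two safeguards are affected. The change should be made because a participant-safety rule is involved and correcting it is cheap.

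**What to change.** Replace the opening words of the supervision sentence in Ethical Considerations so that both promises, the physician on ten-minute call and the CPR/AED C-certified data collector, apply at all five visits, with the screening visit named explicitly. Then check that the emergency action plan in box 9.8.A agrees; if it already covers day one, only this sentence needs to change.

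The cost is one sentence and an extension of the existing on-call arrangement to screening visits. It does not require a physician to be present in the lab. The drawback is that screening visits must be booked when a physician is on call and a certified person is collecting data.
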